### 18.2.1. LABORATORY SPECIFIC DERIVATIONS

- Homeostatic Model Assessment of Insulin Resistance (HOMA-IR) will be calculated for each visit:

$$\text{HOMA IR} = \text{Glucose (mg/dL)} \times \text{Insulin (mU/L)} / 405$$

The following conversion factors will be used if needed:

$$\text{Glucose (mg/dL)} = \text{Glucose (mmol/L)} \times 18.015588;$$

$$\text{Insulin (mU/L)} = \text{Insulin (pmol/L)} \times (1/6).$$

### 18.2.2. LABORATORY REFERENCE RANGES

Laboratory reference range indicators will be provided by the laboratory vendor and used in statistical analyses. Only if a reference range indicator is missing in the data transfer will it be derived in the analysis step as described below.

- Quantitative laboratory measurements (that are not urinalysis erythrocytes or urinalysis leukocytes) will be compared with the relevant laboratory reference ranges in original units and categorized as:
  - Low: Below the lower limit of the laboratory reference range.
  - Normal: Within the laboratory reference range (upper and lower limit included).
  - High: Above the upper limit of the laboratory reference range.
- For laboratory parameters with categorical outcomes as well as urinalysis erythrocytes and urinalysis leukocytes, if the result is within the reference range, the indicator is "NORMAL"; if the result is not within range, the indicator is "ABNORMAL".

## 18.3. ECG EVALUATIONS

Data from the centrally over-read ECG (Electrocardiogram) results will be included in the reporting of this study.

The following ECG parameters will be reported for this study:

- PR Interval (msec)
- RR Interval (msec)
- QRS Duration (msec)
- QRS Axis (deg)
- QT Interval (msec)
- QTcF Interval (msec) (Fridericia's Correction of QT interval)
- QTcB Interval (msec) (Bazett's Correction of QT interval)

- Heart Rate (bpm)
- Overall assessment of ECG as determined by the central over-read:
  - Normal
  - Abnormal, Insignificant
  - Abnormal, Potentially Significant
  - Abnormal, Significant
  - Exclusion Alert (only given for the Screening visit of core study). In table summaries, the category of "Exclusion Alert" will be combined into the category of "Abnormal, Significant".
  - Not Evaluable
- ECG findings

ECG findings will only be listed. Other ECG data will be summarized in tables as well as presented in listings.

The following summaries will be provided:

- For quantitative measurements: By-visit summary of observed values at DB Baseline, OL Baseline, each scheduled OLE study visit (starting from Visit 2E, Visit 1EJ for Japan subjects), and LOCF; by-visit summary of change from DB Baseline at each scheduled OLE study visit (starting from Visit 1E) and LOCF; by-visit summary of change from OL Baseline at each scheduled post-OL Baseline extension study visit (starting from Visit 2E, Visit 1EJ for Japan subjects) and LOCF.
- For ECG overall assessment results as determined by the central over-read ("Normal", "Abnormal, not Clinically Significant (NCS)", "Abnormal, Clinically Significant (CS)", "Not Evaluable"): By-visit summary of number and percentage of subjects in each category at DB Baseline, OL Baseline, each scheduled OLE study visit (starting from Visit 2E, Visit 1EJ for Japan subjects), and LOCF.
- Shift in ECG overall assessment as determined by the central over-read from DB Baseline to each scheduled OLE study visit (starting from Visit 1E) and LOCF, and shift from OL Baseline to each post-OL Baseline extension study visit (starting from Visit 2E, Visit 1EJ for Japan subjects) and LOCF.
- Number and percentage of subjects who met each of the QTc interval prolongation criteria (see [Section 18.3.1](#)) considering both DB Baseline and OL Baseline. The period of evaluation includes both the OLE treatment period and the OLE follow-up period up to and including 7 days post the last OLE dose, including unscheduled visits.
- Number and percentage of subjects with at least one PCS ECG value (see [Table 3](#) in Section 18.3.1) post-OL Baseline. The period of evaluation includes both the OLE treatment period and the OLE follow-up period up to and including 7 days post the last OLE dose, including unscheduled visits. Subjects will be counted in a particular PCS category if they met that PCS criteria at least once during the period of evaluation, regardless of their OL or DB Baseline value.

All ECG parameters, overall assessment as determined by the central over-read, and findings will be provided in a data listing. In addition, separate listings will be generated to present the QTc interval data of subjects who met at least one QTc prolongation criterion and the ECG data that met the PCS criteria.

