15.4.3.4. ECGs

Standard 12-lead ECG parameters heart rate (HR), PR interval, RR interval, QT interval, QTcB and QTcF intervals, and QRS duration will be assessed. Results of each ECG parameter and their changes from DB Baseline and OL Baseline will be summarized by study visit and analysis group using descriptive statistics.

For overall ECG assessment, shift from DB Baseline and shift from OL Baseline will be summarized by study visit for each analysis group.

The number and percentage of subjects with elevated QTc intervals (> 450 msec for males, > 470 msec for females, > 450 msec, > 480 msec and > 500 msec for both males or females) and changes from Baseline in QTc intervals \geq 30 msec, \geq 30 msec but < 60 msec, and \geq 60 msec will be summarized by study visit and overall by analysis group. For other ECG parameters, subjects will be classified as normal or abnormal (details will be provided in the SAP). Number and percentage of subjects with PCS ECG values will be summarized by study visit and for assessment period (treatment-emergent) for each analysis group. Details of ECG PCS criteria will be provided in the SAP.

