## 4.7. CHANGES TO ANALYSIS FROM PROTOCOL

Because of the small sample size due to study early termination, the following main changes will be made for this study:

- Only 2 treatment groups will be formed based on a subject's previous participation in the lead-in study of SEP-4199 CR (SEP-SEP: previously randomized to any SEP-4199 CR dose group and PBO-SEP: previously randomized to placebo).
- No subgroup summaries will be performed.
- No summaries using Follow-up population will be performed.
- Except for PWC, follow-up period summaries will not be performed, PWC will be summarized by Safety population.
- AE will not be summarized by high-level term (HLT).
- No Kaplan-Meier curves will be plotted for time to discontinuation and time to the earliest onsets of the selected AESI. The Kaplan-Meier estimation will also not be performed.
- To be consistent with AIMS and BARS, MSAS will be summarized by total score.

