### 18.3.1. ECG POTENTIALLY CLINICALLY SIGNIFICANT CRITERIA

QTc interval prolongation in adult subjects will be identified in accordance with the following predefined Potentially clinically significant criteria (same criteria apply to both QTcF and QTcB):

- > 450 msec for males \ > 470 msec for females at any post-OL Baseline time point (including unscheduled visits) not present at DB Baseline
- > 450 msec for males \ > 470 msec for females at any post-OL Baseline time point (including unscheduled visits) not present at OL Baseline
- > 480 msec at any post-OL Baseline time point (including unscheduled visits) not present at DB Baseline
- > 480 msec at any post-OL Baseline time point (including unscheduled visits) not present at OL Baseline
- > 500 msec at any post-OL Baseline time point (including unscheduled visits) not present at DB Baseline
- > 500 msec at any post-OL Baseline time point (including unscheduled visits) not present at OL Baseline
- $\geq 30$  msec increase from DB Baseline for at least one post-OL Baseline measurement (including unscheduled visits) and < 60 msec increase from DB Baseline for all post-OL Baseline measurements (including unscheduled visits)
- $\geq 30$  msec increase from OL Baseline for at least one post-OL Baseline measurement (including unscheduled visits) and < 60 msec increase from OL Baseline for all post-OL Baseline measurements (including unscheduled visits)
- $\geq 60$  msec increase from DB Baseline for at least one post-OL Baseline measurement (including unscheduled visits)
- $\geq 60$  msec increase from OL Baseline for at least one post-OL Baseline measurement (including unscheduled visits)

Except for the potentially clinically significant QTc criteria as described above, the PCS ECG measurements will be identified in accordance with the following predefined PCS criteria:

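### SAP 18.3 drops the protocol's by-visit QTc and PCS ECG counts and the both-sexes >450 msec category, and adds a baseline condition, without declaring any of it in SAP 4.7

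*SAP*

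**What the plan says.** Protocol 15.4.3.4 names the absolute QTc categories: above 450 msec for males, then "> 470 msec for females, > 450 msec, > 480 msec and > 500 msec for both males or females". It names three change categories: at least 30, at least 30 but below 60, and at least 60 msec. These counts "will be summarized by study visit and overall by analysis group". It attaches no condition on the baseline value to the absolute categories. It separately promises PCS ECG counts both by visit and for the assessment period. It leaves to the SAP only the normal/abnormal rules for other ECG parameters and the PCS criteria.

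SAP 18.3 plans the "Number and percentage of subjects who met each of the QTc interval prolongation criteria", without a visit level, and says: "The period of evaluation includes both the OLE treatment period and the OLE follow-up period", the latter up to 7 days after the last dose. SAP 18.3.1 words the absolute criteria as in "> 480 msec at any post-OL Baseline time point (including unscheduled visits) not present at DB Baseline", each paired with an OL Baseline version. The only 450 msec criterion is sex-specific; for women it reads "> 470 msec for females at any post-OL Baseline time point (including unscheduled visits) not present at OL Baseline". PCS ECG values (SAP Table 3) are counted if met at least once in the same period.

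SAP 4.7 says that, because of the small sample, "the following main changes will be made for this study". Its list covers analysis groups, subgroups, the follow-up population, follow-up period summaries, HLT tables, Kaplan-Meier curves and MSAS scoring. It contains no ECG item.

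**The concern.** The primary objective is long-term safety, and QTc is a central risk in this protocol. Section 4.3 justifies the CR formulation partly by less QTc prolongation than the IR formulation. Section 10.1.1 makes dose increases conditional on QTcF, and Section 13.1 attaches mandatory discontinuation to QTcF thresholds. The QTc outlier tables are therefore outputs that a safety reader will look for, and the protocol had already fixed their thresholds and their visit level.

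Two things are at stake. First, the tables would no longer show how many subjects exceeded each threshold at each visit. Second, some subjects whom the protocol counts would appear in no QTc count and would not trigger the outlier listing, and a reader of SAP 4.7 would not know that the definition had been narrowed.

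**Working it through.** The plan states no figure to reproduce on this point, so the check is a comparison of the two texts followed by a test of the rules on example subjects.

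**Side by side**

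| Item | Protocol 15.4.3.4 | SAP 18.3 / 18.3.1 | Declared in SAP 4.7? |
|---|---|---|---|
| Level of QTc counts | each visit and overall | one count over the evaluation period | no |
| >450 male / >470 female | no baseline condition | only if not present at DB (or OL) Baseline | no |
| >450, both sexes | yes | absent | no |
| >480 and >500, both sexes | no baseline condition | only if not present at DB (or OL) Baseline | no |
| Increase ≥30 to <60, and ≥60 | each visit and overall | over the period, from each baseline | no |
| Increase ≥30 | each visit and overall | no row of its own | no |
| PCS ECG values | each visit and for the period | at least once in the period | no |

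The overall ≥30 msec count can be recovered: for a given baseline the two SAP change categories are mutually exclusive, and their sum is the number of subjects with any increase ≥30. The by-visit count cannot be recovered from the tables.

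The baseline condition is not a general SAP convention. SAP 18.3 counts the Table 3 PCS values regardless of either baseline.

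**Loss of the visit level.** ECGs are scheduled at Visits 2E to 14E, which is 13 on-treatment visits, or 14 with Visit 15E (Protocol Table 2). Suppose 4 of the 64 enrolled subjects (4/64 = 6.25%) meet a criterion at some scheduled visit. That is compatible with anything from 4 × 1 = 4 to 4 × 14 = 56 positive subject-visits, in any order. The table would read the same in each case.

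**Who drops out of the counts.** The QTc values below are assumed for illustration, and DB and OL Baseline are taken as equal.

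- Woman, baseline 430, highest later value 455. Protocol: 455 > 450, counted. SAP: 455 ≤ 470, so no absolute criterion is met; the increase is 455 − 430 = 25 < 30, so no change criterion is met. Not counted.
- The same woman reaching 465. The increase is 465 − 430 = 35, so the SAP counts her in the ≥30 to <60 category. The gap for women is therefore limited to increases below 30.
- Woman, baseline 460, later 468. Protocol: counted above 450. SAP: 468 ≤ 470 and 468 − 460 = 8 < 30. Not counted.
- Man, baseline 455, later 460 and 470. Protocol: counted above 450. SAP: the 450 msec criterion was already present at both baselines, 470 ≤ 480, and 470 − 455 = 15 < 30. Not counted.

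The same logic removes women already above 470 msec at both baselines who stay at or below 480 msec with increases below 30. Such subjects are also missing from the outlier listing, because SAP 18.3 restricts it to subjects who met at least one QTc criterion. They remain in the full ECG listing only.

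**The case against.** The strongest reply has four parts.

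**Size of the study.** It ended early, with 64 enrolled against about 355 planned (64/355 = 18%). SAP 4.7 trims outputs for that reason, and its heading claims only the main changes. Sparse by-visit tables add little at this size. This supports a decision to omit them, but not silence about it: the list goes down to HLT tables and MSAS scoring, and SAP 18.3 still keeps by-visit counts and shifts for the overall ECG assessment.

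**Timing is available elsewhere.** A reader might infer that the SAP leaves the timing of QTc prolongation unreported. The documents do not support that. SAP 18.3 keeps observed values by visit and a "by-visit summary of change from OL Baseline at each scheduled post-OL Baseline extension study visit" for QTcF and QTcB, and SAP Appendix 1 provides for minimum and maximum. The by-visit maximum shows whether anyone exceeded 480 or 500 msec, or rose by 60 msec or more, at that visit. SAP 7.4 puts original dates and visits in the listings, which are readable for 64 subjects. This part stands. What is missing is how many subjects, and, for the sex-specific thresholds, which sex.

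**PCS criteria were left to the SAP.** SAP 18.3.1 labels the QTc criteria as PCS criteria. But the protocol states the QTc categories itself, separately from the PCS sentence, and promises a visit level for both.

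**Per-visit use of 18.3.1.** Its criteria are defined across visits (any time point, at least one measurement, all measurements), so they cannot simply be tabulated by visit. This is correct, and the fix has to define visit-level counts of its own.

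**Conclusion.** The departure from the protocol is real, specific and undeclared. SAP 18.3 and 18.3.1 drop the by-visit QTc outlier and change counts, the by-visit PCS ECG counts and the both-sexes >450 msec category, and they add a baseline condition to the absolute thresholds.

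The consequence is limited. Timing of outliers must be read from listings and by-visit descriptive statistics, and the subjects described above enter no QTc count and no outlier listing. This assumes that the stated conditions hold on both QTcF and QTcB, since meeting a criterion on either would bring a subject in. The documents do not allow an estimate of how many of the 64 subjects are affected. The study is descriptive, so no inference is invalidated.

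Two further inferences are tempting and should not be drawn. One is that restored by-visit counts would show whether outliers cluster after dose increases. The protocol's counts are by lead-in analysis group, and the dose can rise at Visit 2E or later and fall again, so a visit does not identify a dose. The other is that a whole-period count is a defect because it grows with the number of ECGs. Any such incidence does, and the protocol itself asks for an overall count beside the by-visit ones.

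**What to change.** In SAP 18.3 add, for QTcF and for QTcB, the number and percentage of subjects:

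- with an observed value >450 msec (male) / >470 msec (female), and >450, >480 and >500 msec irrespective of sex, in each case regardless of Baseline;
- with a change from DB Baseline, and separately from OL Baseline, of ≥30, ≥30 to <60 and ≥60 msec.

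Evaluate both at each scheduled visit and overall. The by-visit denominator is subjects with a QTc value at that visit and, for changes, also at the relevant baseline. Keep the existing whole-period treatment-emergent criteria of 18.3.1 alongside. Add by-visit counts for the Table 3 PCS criteria.

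In SAP 4.7 list any of these that remain omitted, with the reason, and declare the added baseline condition.

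The cost is one or two sparse tables from data already collected. There are 4 absolute rows and 3 × 2 = 6 change rows, so 10 rows. Over 2 corrections, 13 on-treatment visits and 3 columns that is 10 × 2 × 13 × 3 = 780 cells. The four PCS limits in Table 3 add 4 × 13 × 3 = 156. If the sponsor judges this too much for 64 subjects, the least that is needed is the overall both-sexes >450 msec row, overall counts regardless of Baseline, and the SAP 4.7 entry.

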### 18.3.1. ECG POTENTIALLY CLINICALLY SIGNIFICANT CRITERIA

QTc interval prolongation in adult subjects will be identified in accordance with the following predefined Potentially clinically significant criteria (same criteria apply to both QTcF and QTcB):

- > 450 msec for males \ > 470 msec for females at any post-OL Baseline time point (including unscheduled visits) not present at DB Baseline
- > 450 msec for males \ > 470 msec for females at any post-OL Baseline time point (including unscheduled visits) not present at OL Baseline
- > 480 msec at any post-OL Baseline time point (including unscheduled visits) not present at DB Baseline
- > 480 msec at any post-OL Baseline time point (including unscheduled visits) not present at OL Baseline
- > 500 msec at any post-OL Baseline time point (including unscheduled visits) not present at DB Baseline
- > 500 msec at any post-OL Baseline time point (including unscheduled visits) not present at OL Baseline
- $\geq 30$  msec increase from DB Baseline for at least one post-OL Baseline measurement (including unscheduled visits) and < 60 msec increase from DB Baseline for all post-OL Baseline measurements (including unscheduled visits)
- $\geq 30$  msec increase from OL Baseline for at least one post-OL Baseline measurement (including unscheduled visits) and < 60 msec increase from OL Baseline for all post-OL Baseline measurements (including unscheduled visits)
- $\geq 60$  msec increase from DB Baseline for at least one post-OL Baseline measurement (including unscheduled visits)
- $\geq 60$  msec increase from OL Baseline for at least one post-OL Baseline measurement (including unscheduled visits)

Except for the potentially clinically significant QTc criteria as described above, the PCS ECG measurements will be identified in accordance with the following predefined PCS criteria:

**Table 3: Predefined ECG PCS criteria.**

ECG Parameter	PCS Low	PCS High
Heart Rate (beats/min)	< 50	> 100
PR Interval (msec)	--	> 210
QRS Interval (msec)	--	> 120

## 18.4. VITAL SIGNS

The following vital sign measurements will be reported for this study:

- Supine and Standing Systolic Blood Pressure (mmHg)
- Supine and Standing Diastolic Blood Pressure (mmHg)

- Supine and Standing Pulse Rate (bpm)
- Respiratory Rate (breaths/min)
- Temperature (°C)
- Weight (kg)
- BMI (kg/m^2)
- Waist Circumference (cm)

Height will be summarized as part of the Baseline characteristics only.

The following summaries will be provided:

- By-visit summary of observed values at DB Baseline, OL Baseline, each scheduled OLE study visit (starting from Visit 2E), and LOCF; by-visit summary of change from DB Baseline at each scheduled OLE study visit (starting from Visit 1E) and LOCF; by-visit summary of change from OL Baseline at each scheduled post-OL Baseline extension study visit (starting from Visit 2E) and LOCF.
- Number and percentage of subjects with at least one PCS vital sign value (see [Section 18.4.2](#)) post-OL Baseline. The period of evaluation includes both the OLE treatment period and the OLE follow-up period up to and including 7 days post the last OLE dose, including unscheduled visits. Subjects will be counted in a particular PCS category if they met that PCS criteria at least once during the period of evaluation, regardless of their DB Baseline or OL Baseline value.
- Number and percentage of subjects with orthostatic hypotension and/or orthostatic tachycardia (see [Section 18.4.1](#)). The data will be summarized for DB Baseline, OL Baseline, overall post-OL Baseline extension period (which covers both the OLE treatment period and the OLE follow-up period up to and including 7 days post the last OLE dose, including unscheduled visits), each scheduled OLE study visit (starting from Visit 2E), and LOCF.
- By-visit summary of BMI category (see [Section 12](#)) at DB Baseline, OL Baseline, each scheduled OLE study visit (starting from Visit 2E), and LOCF.

All vital signs data will be provided in a data listing. In addition, a separate listing will be generated to present the vital signs data that met the PCS criteria. All occurrences of orthostatic hypotension and orthostatic tachycardia will also be presented in a listing.

#### 18.4.1. VITAL SIGNS SPECIFIC DERIVATIONS

- BMI expressed in kg/m^2 = Weight (kg)/ [height (cm)/100].

The height collected at Visit 1 in SEP380-301 will be used to derive BMI where needed throughout the study.

- Orthostatic hypotension is defined as a decrease of  $\geq 20$  mmHg in systolic blood pressure or  $\geq 10$  mmHg in diastolic blood pressure after a subject has been standing for at least 2 to 4 minutes, compared to the systolic blood pressure and diastolic blood pressure measured in the supine position, respectively.

- Orthostatic tachycardia is defined as a heart rate increase of  $\geq 20$  bpm after a subject has been standing for at least 2 to 4 minutes compared to the heart rate measured in the supine position, and a heart rate of  $> 100$  bpm after the subject has been standing for at least 2 to 4 minutes.

#### 18.4.2. VITAL SIGN POTENTIALLY CLINICALLY SIGNIFICANT CRITERIA

Potentially clinically significant vital sign measurements will be identified in accordance with the following predefined PCS criteria, considering both DB Baseline and OL Baseline:

**Table 4: Predefined vital sign PCS criteria**

Vital Sign Parameter	PCS Low	PCS High
Systolic Blood Pressure (Supine, Standing) (mmHg)	Value $\leq 90$ and $\geq 20$ decrease from DB/OL Baseline	Value $\geq 180$ and $\geq 20$ increase from DB/OL Baseline
Diastolic Blood Pressure (Supine, Standing) (mmHg)	Value $\leq 50$ and $\geq 15$ decrease from DB/OL Baseline	Value $\geq 105$ and $\geq 15$ increase from DB/OL Baseline
Pulse Rate (Supine, Standing) (beats/min)	Value $\leq 50$ and $\geq 15$ decrease from DB/OL Baseline	Value $\geq 120$ and $\geq 15$ increase from DB/OL Baseline
Respiration Rate (breaths/min)	Value $\leq 10$ and $\geq 50\%$ decrease from DB/OL Baseline	Value $\geq 25$ and $\geq 50\%$ increase from DB/OL Baseline
Weight (kg)	$\geq 7\%$ decrease from DB/OL Baseline	$\geq 7\%$ increase from DB/OL Baseline
Temperature (°C)	NA	Value $\geq 38.3^{\circ}\text{C}$ and $\geq 0.8^{\circ}\text{C}$ increase from DB/OL Baseline

